4.2.4 Starting Dose and Modifications

4.2.4.1 Nivolumah

The Nivolumab dose if 480 mg IV every 4 weeks.

Adverse events (both non-serious and serious) associated with nivolumab exposure may represent an immunologic etiology. These adverse events may occur shortly after the first dose or several months after the last dose of treatment. Nivolumab must be withheld for drug-related toxicities and severe or life-threatening AEs as per table 3 below. See Section 4.3.1 for supportive care guidelines, including use of corticosteroids.

At the end of the study period, Bristol-Myers Squibb Company will not continue to supply study drug to subjects/investigators unless the Sponsor-Investigator chooses to extend the study. The treating physician is responsible to ensure that the subject receives appropriate standard of care or other appropriate treatment.

No modifications in the dose of nivolumab are permitted. Dose delays are permitted, as outlined below.

Table 3: Nivolumab Dose Delay and Discontinuation Guidelines for Drug-Related Adverse Events

Toxicity	Hold Treatment for Grade	Timing for Restarting Treatment	Treatment Discontinuation
Diarrhea/Colitis	2-3	Toxicity resolves to Grade 0-1	Toxicity does not resolve within 12 weeks of last dose or inability to reduce corticosteroid to 10 mg or less of prednisone or equivalent per day within 12 weeks

Toxicity	Hold Treatment for Grade	Timing for Restarting Treatment	Treatment Discontinuation
	4	Permanently discontinue	Permanently discontinue
AST, ALT, or Increased	2	Toxicity resolves to Grade 0-1	Toxicity does not resolve within 12 weeks of last dose
Bilirubin	3-4	Permanently discontinue (see exception below) ^a	Permanently discontinue
Type 1 diabetes mellitus (if new onset) or Hyperglycemia	T1DM or 3-4	Hold for new onset Type 1 diabetes mellitus or Grade 3-4 hyperglycemia associated with evidence of beta cell failure	Resume when patients are clinically and metabolically stable
Hypophysitis	2-4	Toxicity resolves to Grade 0-1. Therapy with can be continued while endocrine replacement therapy is instituted	Toxicity does not resolve within 12 weeks of last dose or inability to reduce corticosteroid to 10 mg or less of prednisone or equivalent per day within 12 weeks
Hyperthyroidism	3	Toxicity resolves to Grade 0-1	Toxicity does not resolve within 12 weeks of last dose or inability to reduce corticosteroid to 10 mg or less of prednisone or equivalent per day within 12 weeks

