6.2 Safety monitoring

The combination of pembrolizumab plus axitinib has been approved by FDA for advanced renal cell carcinoma, and its toxicity profile has been well established. In this study, we will use nivolumab in place of pembrolizumab, and we expect these two drugs are very similar, thus we expect the toxicity rate of the current combination therapy and dose is acceptable, so we don't think it necessary to conduct a phase I dose-finding study. However, to be cautious, we will 1) use a Bayesian monitoring scheme and 2) incorporate a trial stopping rule into the protocol. The Bayesian monitoring scheme will continuously monitor the rate of severe adverse events (SAE). The SAE is defined as grade 3 and higher toxicity that are attributable to the combination therapy. A non-informative prior of Beta(1, 1) for the SAE rate will be used. We will hold the recruit if the posterior probability Pr(SAE rate>30%)>=0.7 and the study committee and the PI will decide whether to modify or discontinue the study. The stopping boundary for toxicity is given in the following table:

Number of SAEs >=	in Number of Patients =
2	3-5
3	6-8
4	9-11
5	12-14
6	15-17
7	18-20
8	21-23
9	24-26

10	27-29
11	30-31

We simulate the operating characteristics under various assumed true toxicity rate (see the following table):

Scenario	True Prob.	Prob. of	Average	Average
	of SAE	Early	Num. of Patients	Num. of SAE
		Stopping	Patients	SAE
1	0.1	0.10	28	3
2	0.2	0.37	22	4
3	0.3	0.71	14	4
4	0.4	0.93	8	3

Regarding the analysis of safety, we will consider a toxicity event to be an adverse event (evaluated by CTCAE 5.0) that is possibly, probably, or definitely related to treatment. The maximum grade of toxicity for each category of interest will be recorded for each patient and the summary results will be tabulated by category and grade.

If one Grade 5 event or two Grade 4 events for AEs considered at least possibly related to combination study therapy (possibly attributed to each drug) occur, the trial will be halted to accrual and a thorough safety analysis will be conducted prior to enrolling new patients.

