6.3 Sample Size and Accrual

The null hypothesis that the true ORR is 10% will be tested versus a one-sided alternative of 25% or higher, using Simon's minimax two-stage design. In the first stage, 16 patients will be accrued. If there are <2 responses, the study will be stopped and alternative doses of axitinib considered. If at least 2 responses are observed, 15 additional patients will be enrolled in the 2nd stage. The combination therapy will be regarded as worthy of further study if ≥6 responses are observed in both stages. Total sample size is 31 patients. This design has a type I error rate of 0.08 with a power of 0.81 when the true response rate is 0.25. Secondary endpoints of this study are PFS, OS and safety. Survival endpoints (PFS and OS) will be estimated with the Kaplan-Meier method, and compared between marker value groups with the log-rank test. We will also perform extensive correlative analysis (flow, IHC, metabolic analyses).

The accrual rate of the trial is estimated to be 1-2 patients/month, therefore, we will be able to finish the accrual of the study in approximately 24 months.

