6.4 Statistical Analysis Plan

6.4.1 Analysis Sets

DLT evaluable patients are study-eligible patients (i.e., those meeting all of the protocol inclusion/exclusion criteria) who have finished one cycle of the regimen without a DLT, and those who received at least one dose of the regimen and experienced DLT in the first cycle.

Response evaluable patients are study-eligible patients (i.e., those meeting all of the protocol inclusion/exclusion criteria) who have received the regimen and stayed on study long enough for at least one follow-up of response. Patients who didn't come back for scan but clinically progressed will also be considered as evaluable for response, and the best response for these patients is progressive disease.

Safety population - all study eligible patients who received any dose of the study drug will be included in the safety population.

Efficacy population - the data from all treated patients will be used in the intent to treat analyses of tumor response and survival (progression-free and overall). Patients who complete at least one cycle of the treatment will be included in the per-protocol analysis of bioactivity endpoint. Patients who are considered non-compliant are not evaluable for the per-protocol analysis of the primary efficacy endpoint, but still evaluable for safety analysis, so they will be replaced for the primary efficacy analysis.

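### The Section 6.2 toxicity boundary has no observation window and no defined denominator, so its printed stopping probabilities hold only if every outcome is known at once

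*Combined protocol and SAP*

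**What the plan says.** Section 6.2 describes the monitored event this way: "The SAE is defined as grade 3 and higher toxicity that are attributable to the combination therapy". No time limit is attached. On the prior it says: "A non-informative prior of Beta(1, 1) for the SAE rate will be used". The action rule is "We will hold the recruit if the posterior probability Pr(SAE rate>30%)>=0.7", applied continuously. The boundary table pairs a number of events with a count headed "in Number of Patients", starting at 2 events in 3–5 patients and ending at 11 in 30–31. A second table gives stopping probabilities and average patient numbers for four true rates, with no statement about onset time or accrual.

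Other sections bear on the missing pieces:

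- Section 6.3: "The accrual rate of the trial is estimated to be 1-2 patients/month".
- Section 4.2.3 allows treatment for up to 2 years.
- Section 4.2.4.1, on nivolumab toxicity: "These adverse events may occur shortly after the first dose or several months after the last dose of treatment". Section 4.2.5 also mentions late-onset immune toxicity.
- Section 6.4.1 defines a safety population (eligible, any dose, no minimum follow-up). It also defines a DLT-evaluable set containing patients "who have finished one cycle of the regimen without a DLT" plus those with a DLT in cycle 1. Section 6.2 refers to neither, and it counts Grade 3+ toxicity rather than DLTs.
- Adverse-event collection ends 28 days after last intake in Section 6.4.3. In Section 5.2 it ends 100 days after cessation, or at new anticancer therapy if earlier.

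**The concern.** A posterior for a toxicity rate treats each patient as a completed yes/no outcome. Under continuous monitoring, a patient dosed yesterday without an event is not yet a completed 'no'. If that patient is counted as one, the observed rate is diluted and the boundary is crossed later or not at all.

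The rule is one of two safeguards that Section 6.2 adds after deciding against a phase I study, and Section 8.1 relies on it to keep the true rate below 30%. If the window and denominator are left open, two teams could apply the same table to the same data and disagree on whether to hold accrual. Readers would also take the printed probabilities as a description of how the trial will behave.

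**Working it through.** **1. The boundary reproduces.** With s events in n patients the posterior is Beta(1+s, 1+n−s). The boundary is the smallest s with Pr(rate > 0.30) ≥ 0.70. It matches the printed table at every n from 3 to 31.

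**2. The operating characteristics reproduce for immediate outcomes.** An exact binomial recursion, checking after each patient from n = 3 to 31 with each outcome known before the next patient is counted, gives:

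| True rate | Stop, printed | Stop, recomputed | Average patients, printed | Average patients, recomputed |
|---|---|---|---|---|
| 0.1 | 0.10 | 0.096 | 28 | 28.5 |
| 0.2 | 0.37 | 0.366 | 22 | 21.9 |
| 0.3 | 0.71 | 0.709 | 14 | 14.0 |
| 0.4 | 0.93 | 0.928 | 8 | 8.2 |

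The average event counts also agree (rate × average patients: 2.9, 4.4, 4.2, 3.3 against the printed 3, 4, 4, 3).

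**3. How one unobserved patient changes the decision.** Pr(Beta(a,b) > 0.3) equals Pr(Binomial(a+b−1, 0.3) ≤ a−1).

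- Two events in 5 patients: Beta(3,4), Pr(Bin(6, 0.3) ≤ 2) = 0.118 + 0.303 + 0.324 = 0.744, so hold.
- The same two events with a sixth patient just dosed: Beta(3,5), Pr(Bin(7, 0.3) ≤ 2) = 0.082 + 0.247 + 0.318 = 0.647, so no hold.

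At 1 to 2 patients per month, a toxicity period of 3 months leaves about 1×3 to 2×3 = 3 to 6 patients only partly observed at any time. A period of 6 months leaves 6 to 12, against a maximum of 31.

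**4. Size of the loss if all enrolled patients count.** Inputs from the documents are the printed boundary, N = 31 and accrual of 1 to 2 per month (31 patients in 24 months is 1.29 per month). Assumptions not in the documents are Poisson accrual, onset uniform over the stated period, and no pause between stages. Results are simulated, with the range running from 1 to 2 patients per month; any-time means that crossings after the last enrolment also count.

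| Onset spread over | Any-time hold, true 40% (printed 0.93) | Average enrolled, true 40% (printed 8) | Any-time hold, true 30% (printed 0.71) |
|---|---|---|---|
| 1 month | about 0.92 | 9–10 | 0.65–0.68 |
| 3 months | 0.87–0.90 | 11–14 | 0.55–0.62 |
| 6 months | 0.80–0.86 | 14–21 | 0.41–0.54 |

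Counting only holds that come before patient 31, and so can still stop someone being enrolled, the worst cells (6 months, 2 per month) are about 0.63 at a true rate of 40% and 0.31 at 30%.

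**5. Alternative denominators.**

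- *Window closed, counted in enrolment order.* For windows of 28 days, 12 weeks and 24 weeks the stopping probabilities return to 0.09–0.10/0.35–0.37/0.70–0.72/0.93. At a true rate of 30% and 1.29 per month, average enrolment is 14.8, 16.7 and 19.2 for the three windows, against 14 printed.
- *Window closed or event already seen* (the form of the DLT-evaluable set). Events enter before non-events, so the rule over-stops. At 1.29 per month and the same three windows it stops with probability 0.74, 0.79 and 0.86 at a true rate of 30% (printed 0.71), and 0.11, 0.15 and 0.21 at 10% (printed 0.10).
- *Event-free patients weighted by the fraction of the window completed.* With a 3-month window and at least 3 effective patients required, stopping is about 0.07–0.10 at a true rate of 10%, 0.68–0.72 at 30% and 0.91–0.94 at 40%. The spread reflects how the minimum is applied and how often the posterior is refreshed. Without the minimum, false holds at 10% rise to about 0.2.

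**The case against.** The strongest reply is that nothing printed is wrong. The boundary and table are exact for the rule as tabulated, and a team that counts only fully observed patients in enrolment order recovers the printed stopping probabilities. That stands as far as it goes. A reader might infer that the plan divides by every enrolled patient, or that the table was miscalculated; the documents support neither. Section 6.2 does not say whether a patient must be enrolled, dosed or evaluable. Counting dosed patients is the likely reading, given continuous monitoring and an any-dose safety population, but it remains an inference.

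The size is also open. No onset distribution is given. If Grade 3+ toxicity falls within the first month the loss is small. The large losses need onset spread over 6 months and accrual at the top of the stated range, whereas 31 patients in 24 months implies about 1.3 per month. The lowest figures also exclude crossings after the last enrolment, which the printed probabilities have no reason to separate. A late crossing could still lead the committee to modify or discontinue the study for patients on treatment. A reader should therefore not take 0.63 or 0.31 as the rule's expected performance.

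Other safeguards exist. Section 6.2 also halts accrual for one Grade 5 or two Grade 4 events at least possibly related to treatment. That rule has no denominator to dilute. If 20% of Grade 3+ events were Grade 4 (an assumption), the two rules together would hold at some time with probability 0.91–0.96 at a true rate of 40% in all the 3- and 6-month cases examined, although up to 18.6 patients on average would be enrolled. Section 8.1 adds monthly review with authority to suspend accrual. These offset part of the loss but do not respond to the Grade 3 rate in the same way.

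Finally, it would overstate the case to call the Bayesian rule the substitute for phase I. Section 6.2 rests that decision on experience with pembrolizumab plus axitinib and adds the rule as a precaution.

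**Conclusion.** The concern holds as a gap in definition with consequences for the printed figures. Section 6.2 specifies neither an observation window nor which patients count. The printed operating characteristics require immediately known outcomes, which treatment of up to 2 years, acknowledged late toxicity and continuing accrual do not provide.

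If under-observed patients count, the hold probability was below the printed value in every delayed-onset case examined. At a true rate of 30% the any-time loss runs from 0.71 − 0.68 = 0.03 (onset within 1 month) to 0.71 − 0.41 = 0.30 (over 6 months at 2 per month). At 40% it runs from about 0.01 to 0.13, with average enrolment rising from 8 to as many as 21. Even the closed-window reading enrols more patients before a hold than the table shows. The direction follows from the structure of the rule; the size depends on the assumed uniform onset and on counting all enrolled patients.

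**What to change.** In Section 6.2, state one observation window for the toxicity count and define the denominator, keeping the 30%/0.7 threshold. Either of two forms would do:

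- count patients in enrolment order once their window has closed, accepting more patients enrolled at the hold; or
- weight each event-free patient by the fraction of the window completed, count each patient with an event as 1, and require at least 3 effective patients before the rule can act.

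Do not borrow the DLT-evaluable form unchanged, because it over-stops. Replace the table with one simulated at 1 and 2 patients per month under stated onset assumptions, showing patients enrolled at the hold and whether crossings after the last enrolment count. Reconcile the 28-day and 100-day collection periods so that the data support the chosen window.

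The cost is SAP wording, one simulation and less favourable printed figures. The sample size and treatment are unaffected. The window also fixes what the 30% rate refers to: a short window leaves late toxicity outside the rule, so the plan should give the reason for its choice.

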6.3 Sample Size and Accrual

The null hypothesis that the true ORR is 10% will be tested versus a one-sided alternative of 25% or higher, using Simon's minimax two-stage design. In the first stage, 16 patients will be accrued. If there are <2 responses, the study will be stopped and alternative doses of axitinib considered. If at least 2 responses are observed, 15 additional patients will be enrolled in the 2nd stage. The combination therapy will be regarded as worthy of further study if ≥6 responses are observed in both stages. Total sample size is 31 patients. This design has a type I error rate of 0.08 with a power of 0.81 when the true response rate is 0.25. Secondary endpoints of this study are PFS, OS and safety. Survival endpoints (PFS and OS) will be estimated with the Kaplan-Meier method, and compared between marker value groups with the log-rank test. We will also perform extensive correlative analysis (flow, IHC, metabolic analyses).

The accrual rate of the trial is estimated to be 1-2 patients/month, therefore, we will be able to finish the accrual of the study in approximately 24 months.

6.4 Statistical Analysis Plan

6.4.1 Analysis Sets

DLT evaluable patients are study-eligible patients (i.e., those meeting all of the protocol inclusion/exclusion criteria) who have finished one cycle of the regimen without a DLT, and those who received at least one dose of the regimen and experienced DLT in the first cycle.

Response evaluable patients are study-eligible patients (i.e., those meeting all of the protocol inclusion/exclusion criteria) who have received the regimen and stayed on study long enough for at least one follow-up of response. Patients who didn't come back for scan but clinically progressed will also be considered as evaluable for response, and the best response for these patients is progressive disease.

Safety population - all study eligible patients who received any dose of the study drug will be included in the safety population.

Efficacy population - the data from all treated patients will be used in the intent to treat analyses of tumor response and survival (progression-free and overall). Patients who complete at least one cycle of the treatment will be included in the per-protocol analysis of bioactivity endpoint. Patients who are considered non-compliant are not evaluable for the per-protocol analysis of the primary efficacy endpoint, but still evaluable for safety analysis, so they will be replaced for the primary efficacy analysis.

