4.2.2 Patient Compliance

Patients will be required to return all bottles of axitinib at the beginning of each 4-week period. The number of tablets remaining will be documented and recorded.

4.2.3 **Duration of Therapy**

Treatment will continue for up to 2 years or until progression of disease or unacceptable toxicities.

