4.5 Subject Withdrawal/Discontinuation Criteria

Subjects may withdraw consent at any time for any reason or be dropped from the trial at the discretion of the investigator should any untoward effect occur. In addition, a subject may be withdrawn by the investigator or the Sponsor if enrollment into the trial is inappropriate, the trial plan is violated, or for administrative and/or other safety reasons.

A subject must be discontinued from the trial for any of the following reasons:

- The subject or legal representative (such as a parent or legal guardian) withdraws consent.
- Confirmed radiographic disease progression

Note: For unconfirmed radiographic disease progression, please see Section 5.2.2

Note: A subject may be granted an exception to continue on treatment with confirmed radiographic progression if clinically stable or clinically improved, please see Section 7.1.2.7.1

- Unacceptable adverse experiences as described in Section 5.2.1.2
- Intercurrent illness that prevents further administration of treatment
- Investigator's decision to withdraw the subject
- The subject has a confirmed positive serum pregnancy test
- Noncompliance with trial treatment or procedure requirements
- The subject is lost to follow-up
- Completed 24 months of uninterrupted treatment with nivolumab or 24 administrations of study medication, whichever is later.

Note: 24 months of study medication is calculated from the date of first dose.

• After trial discontinuation (whether due to subject withdrawal, progression, or dose limiting toxicity), patients will be seen at week 4 for follow up, and then followed once 100 days after the last day of treatment even if they start a new anticancer therapy. Patients will be contacted by phone for survival follow up for up to 5 years.

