5.1.2.5 Tumor Imaging and Assessment of Disease

PET/CT and CT

- -At baseline and week 12, extra-cranial tumor assessment will be conducted with contrast-enhanced PET/CT or CT and applied using RECIST 1.1 criteria.
- -A screening scan will be performed prior to enrollment unless a recent (within 28 days of enrollment) scan is available. Target and non-target lesions must be identified at time of screening scan and the same lesions must be re-assessed at each restaging scan.
- -Repeat PET/CT or CT imaging will be obtained at week 12, and then CT will be obtained at 12 week intervals.
- -Complete response/partial response confirmation assessments must take place at least 4 and up to 12 weeks after the documentation of initial response. If the last radiographic assessment for extra-cranial disease was more than 8 weeks prior to discontinuation from study and progressive disease has not been documented, disease assessment should be obtained at the time of study discontinuation.
- -If patients have PD by RECIST 1.1 criteria, the Immune Related Response Criteria (irRC) will be used for assessment of tumor response for the purposes of managing patients on protocol treatment and decision making for discontinuation of study therapy due to disease progression. These disease assessments will be performed by the investigator with site radiology reading.
- For the purposes of the secondary efficacy endpoint of the study, response assessment based on RECIST 1.1 will be applied as the primary measure and irRC by investigators will be evaluated as a secondary assessment only if patient have PD by RECIST 1.1. If patients have PD by RECIST 1.1 but have SD or PR by irRC, they will be permitted to continue treatment. In order for a patient to continue to receive study treatment beyond progression by RECIST 1.1, in addition to having SD or PR by irRC, patients must not have symptoms or signs of disease progression, including significantly worse laboratory values or a decline in ECOG performance status.
- At the time of radiographic progression of disease, if treatment is to continue beyond PD, patients will be re-consented and adequately informed of all FDA-approved therapy, and potential clinical benefit, that the patient may be foregoing in order to continue receiving the investigational product.

MRI

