6.4.2 Analysis of ORR (Primary)

Overall response rate (ORR) will be estimated by the percentage of patients who achieve CR, PR or SD by RECIST criteria (detailed in Sections 5.1.2.5 and 9.2), with corresponding exact 95% confidence limits being reported. The difference between marker value groups will be examined with Fisher's exact tests.

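### The plan does not say which patients count in the 2/16 and 6/31 decisions, and one clause replaces non-compliant patients in the primary efficacy analysis

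*Combined protocol and SAP*

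**What the plan says.** Section 6.3 sets out a Simon minimax design with a null ORR of 10% and an alternative of 25%. Stage 1 has 16 patients and the trial continues on 2 or more responses. Stage 2 adds 15, and success is 6 or more responses overall. "Total sample size is 31 patients", with a stated type I error of 0.08 and power of 0.81. No analysis set is named.

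Section 6.4.1 describes the efficacy population: "the data from all treated patients will be used in the intent to treat analyses of tumor response and survival". The same paragraph then says that non-compliant patients cannot be evaluated in the per-protocol analysis of the primary endpoint, "but still evaluable for safety analysis, so they will be replaced for the primary efficacy analysis". The section also defines a response-evaluable set, made up of eligible patients who received the regimen and "stayed on study long enough for at least one follow-up of response", but assigns no analysis to it.

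Section 6.4.2 says that the ORR "will be estimated by the percentage of patients who achieve CR, PR or SD by RECIST criteria". It too names no set. (Counting SD as a response is a separate matter and is not used here.)

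On compliance, Section 4.2.2 says "The number of tablets remaining will be documented and recorded" and gives no cut-off. Section 4.5 lists "Noncompliance with trial treatment or procedure requirements" as a reason for discontinuation, separately from unacceptable adverse experiences.

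On early exits, Section 5.1.2.5 says that "disease assessment should be obtained at the time of study discontinuation", but only if the last scan was more than 8 weeks earlier and progression has not been documented. Section 6.4.1 counts clinical progression without a scan as progressive disease.

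**The concern.** One paragraph gives two rules for the same endpoint. Under the first, every treated patient counts. Under the second, read literally, some treated patients are taken out of the primary analysis and others are enrolled in their place. Replacing anyone also takes the number treated above the stated total of 31, and the plan does not say whether a replaced patient still uses one of the 16 or 31 places.

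This matters because each decision turns on a single response: 1 versus 2 of 16, and 5 versus 6 of 31. Suppose 31 patients are treated, 5 respond, and one non-responder is then judged non-compliant and replaced by a patient who responds. The first 31 treated give 5 responses, which fails. The set with the replacement gives 6 of 31, which succeeds. All treated gives 6 of 32, for which the plan has no rule. Analysts following the same text could report different decisions.

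Non-compliance is judged after treatment starts, in an open-label single-arm trial, without a written definition. Nothing prevents that judgement from being related to outcome. The plan also does not say how a patient counts who leaves before the week-12 scan, has not progressed clinically and falls outside the 8-week condition.

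**Working it through.** **Inputs.** From Section 6.3: stage 1 size 16, continue on ≥2; stage 2 size 15, success on ≥6 overall; null 0.10, alternative 0.25. The documents give neither the fraction replaced, g, nor the response rate among those replaced, q. I assume g = 0.05, 0.10 or 0.20 and q = 0, 0.05 or 0.10.

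**The plan's own figures.** The probability of success at response rate p is the sum over x = 2 to 16 of P(X₁ = x) × P(X₂ ≥ 6 − x), with X₁ ~ Bin(16, p) and X₂ ~ Bin(15, p).

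- p = 0.10: 0.0788 (stated 0.08)
- p = 0.25: 0.8053 (stated 0.81)

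The design arithmetic is sound for exactly 16 and then 31 patients from one fixed set.

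**Replacing a fraction g.** Hold the all-treated ORR at the null, 0.10. The patients who remain then respond at p = (0.10 − g·q)/(1 − g), and this p goes into the formula above.

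| q | g = 0.05 | g = 0.10 | g = 0.20 |
|---|---|---|---|
| 0 | p = 0.1053, alpha 0.096 | p = 0.1111, alpha 0.116 | p = 0.1250, alpha 0.175 |
| 0.05 | p = 0.1026, alpha 0.087 | p = 0.1056, alpha 0.097 | p = 0.1125, alpha 0.122 |
| 0.10 | p = 0.10, alpha 0.079 | p = 0.10, alpha 0.079 | p = 0.10, alpha 0.079 |

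The expected number treated to fill 31 places is 31/(1 − g): 32.6, 34.4 or 38.8.

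**Replacing exactly k non-responders.** Each is replaced by a new patient responding at 0.10. A removed non-responder adds nothing to the count, so this is the same as giving the trial k extra patients at unchanged cut-offs. With the k places split at random between stages, alpha is 0.089, 0.100 or 0.112 for k = 1, 2 or 3.

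**All treated counted, cut-off left at 6.** If m replacements are enrolled, every treated patient counts and stage 1 stays at 16, total N is 31 + m. Alpha is 0.088, 0.098, 0.108, 0.118 or 0.129 for m = 1 to 5.

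**The case against.** The best defence is that the replacement sentence concerns only the per-protocol analysis. Its subject is per-protocol evaluability, and replacement is presented as a consequence of that. On this reading two analyses coexist: intent to treat on all treated patients, and per-protocol with replacement. The reading is plausible. It still does not say which analysis drives the Simon decisions, and replacement still enrols patients beyond 31.

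On the intent-to-treat reading, an unassessed treated patient stays in the denominator without a response. That is fair, but it depends on the all-treated set being the decision set, which is the open question.

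Other sections bear on compliance. Section 4.2.5 lists permitted interruptions, a return window and a missed-dose rule. The flow chart in Section 5.1 requires pill counts and a diary. Section 8.1 provides monthly review of deviations. None of these sets a threshold for exclusion from an analysis.

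Two points about size stand. The replacement rates are assumed, and the largest figure (0.175) needs 20% replaced with no responders among them. The inflation also takes the 10% null to apply to all treated patients. Section 3.2.3.1 bases it on responses to ipilimumab after anti-PD1 therapy and does not state the denominator.

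**Conclusion.** The concern holds. Section 6.4.1 gives conflicting rules for the primary analysis, and neither 6.3 nor 6.4.2 resolves them. The sample-size calculation is correct; the set of patients to which it applies is undefined.

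If removal is unrelated to response, type I error stays at 0.079. If one to three non-responders are replaced, it is 0.089 to 0.112. Across the assumed replacement rates of 5% to 20%, it is 0.096 to 0.175 when none of those replaced would respond, and 0.087 to 0.122 when they respond at 5%. These figures show sensitivity and do not predict what will happen. They assume an all-treated ORR of 10% under the null. The need to name the decision set does not depend on them.

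**What to change.** Before the stage 1 count:

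- In Sections 6.3, 6.4.1 and 6.4.2, state that the stage 1 decision, the final decision and the primary ORR use all treated patients: the first 16, then the first 31, to receive any study drug.
- Count non-compliant or unassessed patients as non-responders unless a response was documented, and do not replace them.
- Delete the replacement clause for the primary analysis.
- Keep the response-evaluable and per-protocol rates as labelled sensitivity analyses, with a written definition of non-compliance.

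The cost is SAP wording and possibly a lower reported ORR. No extra patients are needed. Power falls if some treated patients cannot respond and the rest respond at 25%: 0.78, 0.75 or 0.72 with 1, 2 or 3 such patients placed at random between stages, and 0.77, 0.74 or 0.70 if all fall in stage 1. In those cases the all-treated ORR is itself below the design alternative: 0.25 × (31 − m)/31 = 24.2%, 23.4% or 22.6%. If the all-treated ORR is 25%, so that the rest respond at 0.25 × 31/(31 − m), power with random placement is 0.807, 0.808 or 0.810 and nothing is lost.
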